1 INTRODUCTION

1.1 STUDY DESIGN

This is a Phase 3, multicenter, 52-week treatment, parallel-group, double-blind, randomized, placebo-controlled study to investigate the efficacy of dupilumab in adults and pediatrics aged 6 years and older with signs and symptoms of AFRS.

After a screening phase of 2 to 4 weeks, approximately 62 participants with AFRS who satisfy the inclusion and exclusion criteria will be centrally randomized (using permuted block randomization schedule) via Interactive Response Technology (IRT) in a 1:1 ratio to receive either dupilumab or matching placebo. Randomization will be stratified first by age (adults versus adolescents/children [≥ 6 years old]). In adults, randomization will be stratified further by time from last surgery (≤ 2 years [including surgery naive participants], > 2 years), disease pattern (unilateral/bilateral in the endoscopy at screening), and country. In adolescents/children, randomization will not be stratified further.

1.2 OBJECTIVES AND ENDPOINTS

Table 1 - Objectives and endpoints

	Objectives	Endpoints
Primary	
To evaluate the efficacy of treatment with dupilumab to reduce sinus opacification in a population with allergic fungal rhinosinusitis (AFRS)	
Change from baseline in sinus opacifications assessed by computerized tomography (CT) scans using the Lund Mackay (LMK) score at Week 52
Secondary	
To evaluate the efficacy of treatment with dupilumab to reduce sinus opacification in a population with allergic fungal rhinosinusitis (AFRS) at Week 24To assess the efficacy of dupilumab to reduce the need for rescue treatmentsTo evaluate the efficacy of treatment with dupilumab in improving symptoms in AFRSTo evaluate the efficacy of dupilumab to reduce nasal polyp formation in participants with AFRSTo evaluate the efficacy of dupilumab in improving overall symptom severity and quality of life in AFRS	
Change from baseline in sinus opacifications assessed by CT scans using the LMK score at Week 24Proportion of participants who receive SCS for any reason and/or undergo/plan to undergo surgery for AFRS during the planned study treatment periodChange from baseline in monthly average nasal congestion/obstruction score from the Nasal Symptom Diary at Week 24 and Week 52Change from baseline in the monthly average anterior/posterior rhinorrhea score from the Nasal Symptom Diary at Week 24 and Week 52Change from baseline in endoscopic nasal polyp score (NPS) compared with placebo at Week 24 and Week 52Change from baseline in 22-item sino-nasal outcome test (SNOT-22) total score at Week 24 and Week 52

Objectives	Endpoints

• To evaluate the efficacy of dupilumab in improving sense of smell in participants with AFRS• To explore the effect of dupilumab as assessed by three-Dimensional CT volumetric measurement of the paranasal sinuses• To evaluate the safety and tolerability of dupilumab when administered to participants with AFRS• To evaluate the PK of dupilumab in participants with AFRS• To characterize the effect of dupilumab on total IgE and fungal-specific IgE• To assess immunogenicity to dupilumab in participants with AFRS	
• Change from baseline in monthly average total symptom score (TSS) derived from the Nasal Symptom Diary at Week 24 and Week 52• Change from baseline in visual analog scale (VAS) rhinosinusitis at Week 24 and Week 52• Change from baseline in University of Pennsylvania smell identification test (UPSIT) at Week 24 and Week 52• Change from baseline in the score of decreased/loss of smell using the Nasal Symptom Diary at Week 24 and Week 52• Change from baseline to Week 52 in three-Dimensional CT volumetric measurement of the paranasal sinuses• Incidence of treatment-emergent adverse events (TEAEs) or serious adverse events (SAEs) through Week 52• Dupilumab concentration in serum over time• Percent change from baseline in total IgE in serum compared with placebo over the 52-week treatment period• Percent change from baseline in fungal-specific IgE in serum compared with placebo over the 52-week treatment period• Assessment of incidence of treatment-emergent anti-drug antibodies (ADA) to dupilumab over time

Objectives	Endpoints

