1.3 SCHEDULE OF ACTIVITIES (SOA)

Procedure	Screening 2-4 wks D-28 to D-14	Intervention period weeks						Follow-up (Wk 64, 12 weeks after EOT)/EOS ^c	Notes
		Wk 0 D1 ^a	Wk 2 D15 ^x	Wk 12 D85	Wk 24 D169	Wk 36 D252	Wk 52 D364 EOT ^b		
Visit	1	2	3	4	5	6	7	8	Visit window: +3 days for Visit 2, ±3 days for Visits 3 to 7, ±5 days for Visit 8
Screening and baseline									
Informed consent/assent ^d	X								
Inclusion and exclusion criteria	X	X							Recheck clinical status before randomization.
Participant demography	X								
Full physical examination	X	X			X		X		Including skin (full body skin exam), nasal cavities, eyes, ears, respiratory, cardiovascular, gastrointestinal, neurological, lymphatic, and musculoskeletal systems.
Medical/surgical history ^e	X								
Record planned endoscopic sinus surgery ^f	←————→								
Prior/Concomitant medications	X	X	X	X	X	X	X	X	Check INCS as prior medication at screening and background medication during study period. Record rescue therapy, if applicable.
Randomization		X							
Log-in to IRT	X	X	X	X	X	X	X	X	

Procedure	Screening 2-4 wks D-28 to D-14	Intervention period weeks						Follow-up (Wk 64, 12 weeks after EOT)/EOS ^c	Notes
		Wk 0 D1 ^a	Wk 2 D15 ^x	Wk 12 D85	Wk 24 D169	Wk 36 D252	Wk 52 D364 EOT ^b		
Visit	1	2	3	4	5	6	7	8	Visit window: +3 days for Visit 2, ±3 days for Visits 3 to 7, ±5 days for Visit 8
Study intervention^g									
IMP administration ^h									IMP will be administered every 14 ±3 days (q2w) for participant weighing ≥30 kg (measured at screening) or 28±3 days (q4w) for participant weighing <30 kg (measured at screening). Between visits at site, home administration is allowed after appropriate training of the participant (or parent/legally authorized representative, or caregiver). The planned last dose is at Week 50 for q2w injections and Week 48 for q4w injections.
Efficacy assessmentsⁱ									
Nasal Endoscopy ⁱ	X	X		X	X	X	X	X	For participant aged ≥6 to <12 years old, nasal endoscopy will only be mandatory at screening, Week 0, Week 24, and Week 52.
CT scan ^k	X				X		X		Initial CT scan to be done during screening period results should be available prior to randomization (Visit 2). Week 24 CT scan is not required for adolescents/children.

Procedure	Screening 2-4 wks D-28 to D-14	Intervention period weeks						Follow-up (Wk 64, 12 weeks after EOT)/EOS ^c	Notes
		Wk 0 D1 ^a	Wk 2 D15 ^x	Wk 12 D85	Wk 24 D169	Wk 36 D252	Wk 52 D364 EOT ^b		

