- The **treatment-emergent (TE) period** is defined as the period from the first IMP administration to the last IMP administration +98 days. The treatment-emergent period includes the following 2 periods:

- The **on-treatment period** is defined as the period from the first IMP administration to the last administration of the IMP +14 days for adults and adolescents/children ≥ 30 kg at screening or 28 days for adolescents/children ≥ 15 kg and < 30 kg at screening.
- The **residual treatment period** is defined as the period from the end of the on-treatment period to the end of the treatment-emergent period.
- The **post-treatment period** is defined as the period from the end of the treatment-emergent period.

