3.3 SECONDARY ENDPOINT(S) ANALYSIS

The secondary endpoints detailed in this section are secondary efficacy endpoints and selected secondary biomarker endpoint. Other secondary endpoints analyses are defined in [Section 3.6.2](#) (AE, SAE), [Section 3.7.1.1](#) (PK), [Section 3.7.1.2](#) (immunogenicity) and [Section 3.7.1.4](#) (biomarker).

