3.6.2 Adverse events

General common rules for adverse events

All adverse events (AEs) will be coded to a lower-level term (LLT), preferred term (PT), high-level term (HLT), high-level group term (HLGT), and associated primary system organ class (SOC) using the Medical Dictionary for Regulatory Activities (MedDRA) version currently in effect at Sanofi at the time of database lock.

The AEs will be analyzed in the following 3 categories:

- Pre-treatment AEs: AEs that developed, worsened or became serious during the pre-treatment period.
- Treatment-emergent adverse events (TEAE)s: AEs that developed, worsened or became serious during the treatment-emergent period.
- Post-treatment AEs: AEs that developed, worsened or became serious during the post-treatment period.

Similarly, the deaths will be analyzed in the pre-treatment, treatment-emergent and post-treatment periods.

The primary AE analyses will be on TEAEs. Pre-treatment and post-treatment AEs will be described separately.

An AE with incomplete or missing date/time of onset (occurrence, worsening, or becoming serious) will be classified as a TEAE unless there is definitive information to determine it is a pre-treatment or a post-treatment AE.

If the assessment of the relationship to IMP is missing for an AE, this AE will be assumed as related to IMP. Missing severity will be left as missing.

Multiple occurrences of the same event in the same participant will be counted only once in the tables within a treatment phase.

The AE tables will be sorted as indicated in [Table 4](#).

Table 4 - Sorting of AE tables

AE presentation	Sorting rules
SOC, HLGT, HLT and PT	By the internationally agreed SOC order and by alphabetic order of HLGTs, HLTs and PTs.
SOC, HLT and PT	By the internationally agreed SOC order and by alphabetic order of HLTs and PTs.
SOC and PT	By the internationally agreed SOC order and decreasing frequency of PTs ^{a,b}
SMQ/CMQ and PT	By decreasing frequency of SMQs/CMQs and PTs ^a
PT	By decreasing frequency of PTs ^a

^a Sorting will be based on the dupilumab intervention group.

^b The table of all TEAEs presented by primary SOC and PT will define the presentation order for all other tables (eg, treatment-emergent SAE) presented by SOC and PT, unless otherwise specified.

Analysis of all adverse events

The overview of TEAE with the details below will be generated:

- Any TEAE
- Any severe TEAE

- Any treatment-emergent SAE
- TEAE leading to death

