3.8 INTERIM ANALYSES

There is no interim analysis planned as part of this study.

A primary database lock will be performed when all randomized participants have completed or discontinued their treatment phase. Final analyses in the CSR will be based on all data collected up to this database lock.

[figure not shown]
The database will be updated at the end of the study for all participants to include the posttreatment follow-up information and updates for the events previously ongoing at the time of the primary lock. Additional data between this database lock and last participant completing last visit will be summarized in a CSR addendum.

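### The secondary safety endpoint stops at Week 52, but the adverse event tables assigned to it run to last dose +98 days and none is cut at Week 52

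*SAP*

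**What the plan says.** - **Endpoint.** Protocol Table 1 (Section 3) and SAP Table 1 (Section 1.2) give the same wording: "Incidence of treatment-emergent adverse events (TEAEs) or serious adverse events (SAEs) through Week 52".
- **Where it is analysed.** SAP 3.3 says "Other secondary endpoints analyses are defined in" other sections, and names Section 3.6.2 for AEs and SAEs.
- **What is counted there.** SAP 3.6.2 states "The primary AE analyses will be on TEAEs", and TEAEs are "AEs that developed, worsened or became serious during the treatment-emergent period".
- **How long that period is.** Under SAP 3.1 the treatment-emergent period "is defined as the period from the first IMP administration to the last IMP administration +98 days". Its on-treatment sub-period is shorter: it "is defined as the period from the first IMP administration to the last administration of the IMP +14 days for adults and adolescents/children" of at least 30 kg, and runs to +28 days below 30 kg. No adverse event table uses this sub-period.
- **Dosing end.** Protocol 1.3: "The planned last dose is at Week 50 for q2w injections and Week 48 for q4w injections".
- **Lock.** SAP 3.8 places the primary lock at the point where every randomized participant has completed or discontinued treatment, and bases the CSR on everything collected by then. After that, "Additional data between this database lock and last participant completing last visit will be summarized in a CSR addendum". Protocol 9.5 is to the same effect.
- **Declared changes.** Neither the SAP version history nor SAP 3.9 records a change to the safety endpoint.

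**The concern.** A named secondary endpoint should have an analysis that matches its definition. Here the definition has a fixed horizon and the assigned analysis has a different one, which depends on each participant's last dose. Someone reading the CSR safety table as 52-week incidence would be reading something else.

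Two consequences follow.

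- The extra 10 to 12 weeks beyond Week 52 are not fully observed for everyone at the primary lock, so the percentages mix slightly different windows according to date of entry.
- The treatment-emergent period can also end before Week 52 in participants who stop dosing early. An SAE that the endpoint wording appears to include can then fall outside the treatment-emergent SAE tables.

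**Working it through.** **1. Where the windows end.** Day 1 is the first dose, so Week w is Day 7w + 1.

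| Schedule | Planned last dose | On-treatment end | Treatment-emergent end |
|---|---|---|---|
| q2w | Week 50 = Day 351 | 351 + 14 = Day 365 (Week 52) | 351 + 98 = Day 449 (Week 64) |
| q4w | Week 48 = Day 337 | 337 + 28 = Day 365 (Week 52) | 337 + 98 = Day 435 (Week 62) |

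For q2w completers the counted window is 64/52 = 1.23 times the stated one. The on-treatment period ends at Week 52 for completers on either schedule, so the SAP already has a window close to the endpoint for them but does not apply it to adverse events.

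**2. Is any table cut at Week 52?** The overview, Table 5, the death summaries, the AESI and other groupings and the exposure-adjusted rates in SAP 3.6.2 are organised by pre-treatment, treatment-emergent or post-treatment period, or, for some serious events, without regard to period. None has a Week 52 limit.

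**3. Follow-up at the lock.** The last participant to finish treatment has about 52 weeks at lock. Anyone randomized at least 12 weeks earlier can have 64. The documents do not give the accrual period. Assume uniform accrual over A weeks and a lock as soon as the last participant reaches Week 52. The truncated share is then 12/A, and mean follow-up is 64 − 6 × 12/A weeks, because truncated participants lose 6 weeks on average.

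- A = 52: 12/52 = 23%, about 14 of 62; mean 62.6 weeks.
- A = 140: 12/140 = 8.6%, about 5 of 62; mean 63.5 weeks. This is the interval from first randomization (21-May-2021) to SAP approval (22-Jan-2025), 191.7 weeks, less 52.
- A = 160: 12/160 = 7.5%, about 5 of 62; mean about 63.6 weeks.

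**4. Early stoppers.** The treatment-emergent period ends 14 weeks after the last dose, so it ends before Week 52 when the last dose is before Week 52 − 14 = Week 38. Example: a last dose at Week 24 (Day 169) ends the period at Day 267, Week 38. An SAE at Week 45 then goes to the post-treatment SAE table.

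**5. Exposure-adjusted rates.** SAP 3.6.2 produces these only if cumulative treatment exposure is imbalanced between arms, which is a different matter from unequal follow-up at lock. Event-free participants contribute the length of the treatment-emergent period, with no stated truncation at lock. Taken literally, with A = 52, that credits 14.3 × 6/52 = 1.65 unobserved participant-years out of 62 × 64/52 = 76.3.

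**6. Illustrative effect on incidence.** With a constant hazard that continues after dosing stops, and full follow-up to Week 64, p64 = 1 − (1 − p52)^(64/52). The 52-week rates are assumed; the documents give none.

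- 5%: 1 − 0.95^1.231 = 6.1%
- 30%: 1 − 0.70^1.231 = 35.5%
- 70%: 1 − 0.30^1.231 = 77.3%

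**The case against.** The strongest reply is that the +98-day window is deliberate. Protocol 4.2 ties the 12-week follow-up to the time for drug levels to become non-detectable in most participants, and the SAP calls that time residual treatment. For completers it contains the whole 52-week window, so nothing is lost. Safety is descriptive, the endpoint is outside the testing hierarchy in SAP 3.5, and the staged lock is pre-specified. All of this stands. It justifies keeping the treatment-emergent tables, but it does not give the Week 52 endpoint an analysis.

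A reader might also infer more than the documents support.

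- *That TEAEs in early stoppers are wrongly dropped.* An event more than 98 days after the last dose is not treatment-emergent by the SAP's definition, so leaving it out of a TEAE count is consistent. Only the SAE half is affected, and those events are not lost: Table 5 includes post-treatment SAEs, and Protocol 9.4.5 summarizes SAEs outside the treatment-emergent period separately. If the sponsor meant treatment-emergent SAEs only, this part falls away, but the endpoint wording does not say so.
- *That the CSR percentages will be revised in the addendum.* SAP 3.8 says only that later data will be summarized, not that these tables will be rerun.
- *That unequal follow-up biases the comparison.* Truncation depends on calendar date of entry. With 1:1 randomization it favours neither arm in expectation.
- *That both effects can be large together.* The 6.1% and 77% figures need nearly everyone to have 64 weeks. The more participants are truncated at lock, the closer the result is to 52-week incidence.

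**Conclusion.** The mismatch holds on the text of both documents. The endpoint ends at Week 52; its assigned analysis ends at Week 64 for q2w completers and Week 62 for q4w completers; no adverse event table bridges the two; and no change is declared. This needs no assumption beyond completion of dosing as scheduled.

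The unequal window at lock follows from SAP 3.8, but its extent is not known. Under uniform accrual over 52 to 160 weeks it would touch about 14 down to 5 of 62 participants; a later lock would reduce that, and heavier late accrual would raise it. The SAE issue is confined to participants whose last dose falls before about Week 38, and is one of placement in tables, not of missing data.

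The incidence figures are upper-end illustrations under a constant hazard and assumed rates, not predictions. Efficacy inference is unaffected. The consequence is modest, but the correction is cheap and should be made before the lock.

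**What to change.** In SAP 3.6.2, add a table, designated as the analysis of the stated endpoint, giving by arm the number and percentage of participants with:

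- a TEAE with onset from first dose to one fixed Week 52 day; and
- any SAE with onset in the same interval, whether or not it is treatment-emergent.

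Name the day explicitly. Day 365 coincides with the end of the on-treatment period for completers; the visit schedule uses Day 364, so the choice should be stated.

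Keep the treatment-emergent-period tables as they are. State that, for participants still in follow-up, treatment-emergent windows and person-time are truncated at the lock date.

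The cost is one extra cut of existing adverse event data and a sentence or two in the SAP. No new data collection is needed.

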1.2.1 Estimands

Primary estimand defined for main endpoints are summarized below in [Table 2](#). More details are provided in [Section 3](#).

For all these estimands, the comparison of interest will be the comparison of dupilumab versus placebo.

Table 2 - Summary of primary estimand for main endpoints

Endpoint Category	Estimands			
	Endpoint	Population	Intercurrent event(s) handling strategy	Population-level summary (Analysis and missing data handling)
Primary objective: To evaluate the efficacy of treatment with dupilumab to reduce sinus opacification in a population with allergic fungal rhinosinusitis (AFRS)				
Primary endpoint	Change from baseline in LMK score at Week 52	ITT	
The following intercurrent events will be handled with a composite strategy; data after the IE will be excluded and the worst post-baseline value on or before the start of the IE will be assigned to the Week 52 value (WOCF); for participants with no post-baseline values, the baseline value will be used.
 
Undergo/plan to undergo surgery for AFRS prior to Week 52	
Mean difference between interventions in change from baseline in LMK score at Week 52 will be analyzed using ANCOVA model with the baseline LMK score, intervention group, time from last surgery (≤ 2 years, >2 years), and region^a (Americas, Asia) as covariates.
 
In addition, the missing data imputation rules are as follows:

Endpoint Category	Estimands		
	Endpoint	Population	Intercurrent event(s) handling strategy
		
 • Taking SCS for any reason/indication prior to Week 52 
The following IEs will be handled with the treatment policy strategy (without IEs that need to be handled with composite strategy). All assessments after starting such IE will be included.
 
 • Discontinuing the study intervention • Taking antifungals or other prohibited/rescue medications 	
 • After applying the strategies for intercurrent events, if there is still missing data multiple imputation (MI) approach will be used to impute missing endpoint value, and this MI will use all participants excluding participants who have taken SCS for any indication or underwent/plan to undergo surgery for AFRS before Week 52. 
Statistical inference obtained from all imputed data by ANCOVA model will be combined using Rubin's rule.

Secondary objective:

- To evaluate the efficacy of treatment with dupilumab to reduce sinus opacification in a population with allergic fungal rhinosinusitis (AFRS) at Week 24
- To assess the efficacy of dupilumab to reduce the need for rescue treatments
- To evaluate the efficacy of treatment with dupilumab in improving symptoms in AFRS
- To evaluate the efficacy of dupilumab to reduce nasal polyp formation in participants with AFRS
- To evaluate the efficacy of dupilumab in improving overall symptom severity and quality of life in AFRS
- To evaluate the efficacy of dupilumab in improving sense of smell in participants with AFRS
- To explore the effect of dupilumab as assessed by three-Dimensional CT volumetric measurement of the paranasal sinuses
- To characterize the effect of dupilumab on total IgE and specific IgE

Secondary endpoint	Proportion of participants who receive SCS and/or undergo/plan to undergo surgery for AFRS during the planned study treatment period	ITT	
The following IEs will be handled with a treatment policy strategy:
 
 • Discontinuation of study intervention • Taking antifungals or other prohibited/rescue medications 	
Risk difference between interventions will be estimated using Mantel-Haenszel estimate and confidence limits, with Mantel-Haenszel stratum weights for time from last surgery (≤ 2 years, > 2 years) and region^a (Americas, Asia) and the Sato variance estimator. The P-value associated with Mantel-Haenszel method will be provided if appropriate. In addition, the missing data imputation rules are as follows:
 
 • Discontinuing the study follow-up without an event prior to discontinuation: Participant will be considered as no event.
--------------------	--	-----	---	--

Endpoint Category	Estimands			
	Endpoint	Population	Intercurrent event(s) handling strategy	Population-level summary (Analysis and missing data handling)
Secondary endpoint	Continuous secondary efficacy endpoints	ITT	
The following intercurrent events will be handled with a composite strategy; data after the IE will be excluded and the worst post-baseline value on or before the start of the IE will be assigned to the endpoint value
 
(WOCF); for participants with no post-baseline values, the baseline value will be used.
 
 • Undergo/plan to undergo surgery for AFRS prior to endpoint visit • Taking SCS for any reason prior to endpoint visit 
The following IEs will be handled with the treatment policy strategy (without IEs that need to be handled with composite strategy). All assessments after starting such IE will be included.
 
 • Discontinuing the study intervention • Taking antifungals or other prohibited/rescue medications 	
Mean difference between interventions will be analyzed with the same ANCOVA method as the primary endpoint.
 
Same multiple imputation approach will also be used to impute missing data.

Secondary endpoint	Percent change from baseline in total IgE in serum at Week 52	Safety	
The following intercurrent events will be handled with a composite strategy; data after the IE will be excluded and the worst post-baseline value on or before the start of the IE will be assigned to the Week 52 value (WOCF); for participants with no post-baseline values, the baseline value will be used.
 
 • Undergo/plan to undergo surgery for AFRS prior to Week 52 • Taking SCS for any reason prior to Week 52 
The following IEs will be handled with the treatment policy strategy (without IEs that need to be handled with composite strategy). All assessments after starting such IE will be included.
 
 • Discontinuing the study intervention • Taking antifungals or other prohibited/rescue medications 	
Mean difference between interventions will be analyzed with the same ANCOVA method as the primary endpoint.
 
Same multiple imputation approach will also be used to impute missing data.

a Americas: Argentina, USA, Canada; Asia: China, Japan, India, Turkey, Saudi Arabia

